6.6 Mutational Analysis

Note: As of Protocol Version 7/ Amendment 6, samples for mutational analysis are no longer being collected.

Bone marrow aspirate and peripheral blood samples for exploratory assessments of cancer-associated mutations and/or genetic alterations will be collected as follows:

A bone marrow aspirate sample will be collected during the Screening period, prior to Cycle 1 Day 1. If the patient had a bone marrow aspirate performed within 28 days of Cycle 1 Day 1 and there is sufficient sample available for analysis, it does not need to be repeated.

At any time while on treatment, if a patient undergoes a bone marrow aspirate or biopsy sample collection for response assessment, material will be requested for cancer-associated mutations analysis (refer to Section 4.3 and Section 6.3 for timepoint details).

Peripheral blood samples will be collected at Screening and at each timepoint that a bone marrow aspirate or biopsy is obtained.

See the laboratory manual provided for details of the specific analyses and instructions on collecting and processing of these samples.

^a Collected in dose-expansion patients during C2D2 and at the end of 72 hr FT-2102 washout (C2D4) (see Schedule of Events in Appendix 1).

b Not required in Phase 2.

Note: Pretreatment bone marrow aspirate and peripheral blood samples for retrospective confirmation of IDH1m by the central assay is mandatory for efficacy evaluable (EE) population definition, and not an exploratory assessment.

6.7 Outcome Research Assessment

Note: As of Protocol Version 7/ Amendment 6, quality of life assessments are no longer being performed.

Throughout the clinical trial period, patients will be asked about their quality of life via the Quality of Life questionnaires EQ-5D-5L.

The EQ-5D-5L is a standardized instrument developed by the EuroQol Group to describe and value health related quality of life. The instrument comprises the following five dimensions: mobility, self-care, usual activities, pain/discomfort and anxiety/depression. Each dimension is rated by the patients on a 5 point scale as having 'no problems' (a score of 1), 'slight problems (a score of 2), 'moderate problems', (a score of 3), 'severe problems', (a score of 4) and 'extreme problems', (a score of 5) based on descriptive examples: the scores are not intended to be summed. Present overall state of health is also to be rated on a vertical visual analogue scale (approximately 20cm in length) from 0 to 100 (the higher the number the better quality of life.

The EQ-5D-5L will be performed at screening (any time prior to first dose) and then monthly on Day 1 of Cycles 1 to 4 (completed prior to all other D1 procedures) for all Phase 2 patients.

Patients should self-complete the EQ-5D-5L and return to the site. Data will then be entered into the patient's eCRF.

6.8 Dose Modifications

6.8.1 FT-2102 Dose Modifications

Patients participating in the dose-escalation stage who are receiving a dose of FT-2102 that is one level below an established safe dose may be considered for intrapatient dose escalation if they have not experienced a protocol-defined dose limiting toxicity at the lower dose level, and pending a consultation between the Investigators and Medical Monitor.

If a patient has an AE that is judged by the Investigator as related to study drug (i.e., assessed as unrelated to the underlying disease, intercurrent illness, or concomitant medications), then dose modifications can be made according to the guidelines in Table 6. Dose modification guidelines for liver function test (LFT) abnormalities are presented in Table 7. Dose reduction guidelines are presented in Table 8.

Deviations from these guidelines (e.g., drug interruption for a Grade 2 pleural effusion) may occur if agreed upon by the Principal Investigator and Medical Monitor. There should be no attempt to make up doses omitted due to toxicity.

Table 6 FT-2102 Recommended Dose Modifications for Adverse Events Unrelated to Liver Function Abnormalities

Severity of Adverse	Dose Modifications for FT-2102 ^c						
Events	Non-Hematologic	Hematologic					
Grade 1	Continue treatment at the same dose	Continue treatment at the same dose					
Grade 2	Continue treatment at the same dose. If dose interruption is clinically indicated, resume dosing at same dose level after recovery to $\leq G1$	Continue treatment at the same dose					
Grade 3	Hold treatment until recovery to ≤ G1 or baseline, whichever is worse ^a , then resume at the next lower dose level. Contact Medical Monitor if resumption of FT-2102 at full dose is clinically indicated.	Continue treatment at the same dose. If dose interruption is clinically indicated, resume dosing at same dose level after recovery to \leq G2					
Grade 4	Permanently discontinue treatment ^b	Hold treatment until recovery to ≤ G2 or baseline, whichever is worse, then resume at the next lower dose level. Contact Medical Monitor if resumption of FT-2102 at full dose is clinically indicated.					

AE = adverse event.

Table 7 FT-2102 Recommended Dose Modifications for Liver Function Test Abnormalities

Laboratory Abnormality	Action to be Taken with FT-2102
AST or ALT or total bilirubin is Grade 3	Hold FT-2102
AST or ALT is > 3 times the ULN and patient has signs and symptoms of a hypersensitivity reaction not related to underlying disease [e.g., fatigue, nausea, vomiting, RUQ pain or tenderness, fever, rash and/or eosinophilia (>5%)]	Hold FT-2102
For patient with elevated AST or ALT or total bilirubin at baseline: AST or ALT > 2 times baseline AND > 3.0 times ULN OR AST or ALT > 8.0 times ULN- whichever is lower- combined with total bilirubin > 2 times baseline AND > 2 times ULN	Hold FT-2102
AST or ALT is > 3 times the ULN and the total bilirubin is > 2 times ULN and Alkaline phosphatase < 2 times ULN in the absence of a clear alternative explanation	Permanently discontinue FT-2102
AST or ALT or total bilirubin is Grade 4	Permanently discontinue FT-2102

ALT = alanine aminotransferase; AST = aspartate aminotransferase; RUQ = right upper quadrant; ULN = upper limit of normal.

^a In the event of Grade 3 nausea, vomiting, diarrhea, or rash, the patient can continue at the same dose if the patient is responsive to treatment measures within 72 hr.

A patient with a Grade 4 AE may resume treatment at the next lower dose level if the AE recovers to Grade 0-1 or baseline and if in the opinion of the Investigator and Sponsor, the patient can be monitored for recurrence of AF

Dose modification may be more or less conservative at the Investigator's discretion and after consultation with the medical monitor.

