i. Frequent monitoring of AST, ALT, alkaline phosphatase, albumin, INR/PT, and total bilirubin should be initiated. Frequency would be, at minimum, twice per week until asymptomatic and the patient has returned to baseline or Grade 1 toxicity.

Restarting FT-2102 after suspected liver injury:

- a. Once the AE returns to Grade 0-1 or baseline, resume treatment with FT-2102 at 150 mg once daily (see Table 8).
- b. For the next 28 days, while reduced dosing at 150 mg once daily, AST, ALT and total bilirubin should be monitored at minimum twice per week for the first 2 weeks and then weekly if no recurrence of elevations are observed.
- c. If the AE recurs at 150 mg once daily, the patient will be discontinued from study treatment (see Section 6.8.2).
- d. If after a minimum of 28 days of 150 mg once daily, the AST, ALT and total bilirubin have not elevated to Grade 2 or greater and no other symptoms, then FT-2102 may be reescalated to the dose level prior to event.
- e. Frequent monitoring (at least twice per week) is required upon re-escalation, and may be decreased after patient has been on the escalated dose for at least 28 days without an increase in the AST, ALT and total bilirubin.

Patients on active treatment with FT-2102 should be informed to promptly notify study staff if they develop any clinical symptoms of jaundice and to avoid personal habits (excessive ethanol consumption, over-the-counter hepatic injurious medications, herbal medications [e.g., cannabidiol or comparable products]) that may cause additional risk of hepatic injury.

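### The Section 5.5.3 restart rule makes no exception for the two liver findings for which Table 7 stops FT-2102 permanently

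*Protocol*

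**What the plan says.** Table 7 (Section 6.8.1) sets the action on FT-2102 for liver test abnormalities. It has three Hold rows and two permanent-stop rows. Three of the five rows matter most here:

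- **Elevated-baseline Hold row.** For patients with raised AST, ALT or bilirubin at baseline, AST/ALT must exceed both twice baseline and 3 × ULN, or exceed 8 × ULN, whichever is lower, "combined with total bilirubin > 2 times baseline AND > 2 times ULN".
- **Combined-rise stop row.** FT-2102 is permanently discontinued when "AST or ALT is > 3 times the ULN and the total bilirubin is > 2 times ULN". Two further conditions apply: ALP must be below 2 × ULN, and there must be no clear other cause. The row is not restricted to patients with a normal baseline.
- **Grade 4 stop row.** FT-2102 is permanently discontinued when "AST or ALT or total bilirubin is Grade 4".

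Section 5.5.3 has its own list, headed "Restarting FT-2102 after suspected liver injury":

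- Item a: "Once the AE returns to Grade 0-1 or baseline, resume treatment with FT-2102 at 150 mg once daily".
- Item c: "If the AE recurs at 150 mg once daily, the patient will be discontinued from study treatment".
- Item d: after at least 28 days at the reduced dose without a Grade 2 or higher elevation or other symptoms, "then FT-2102 may be reescalated to the dose level prior to event".

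Items a and c cite Table 8 and Section 6.8.2. Nothing in the list cites Table 7.

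**The concern.** Section 5.5.3 and Table 7 both tell a site what to do with FT-2102 after liver injury, and for two findings they differ. Table 7 says the drug is never given again. The restart list says to give it again on recovery, and stops it only if the event recurs at the reduced dose. Two sites could each follow written text and manage the same event in opposite ways, one by rechallenge and the other by a permanent stop.

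The findings in question are an unexplained joint rise in AST/ALT and bilirubin without marked ALP elevation, and a Grade 4 value. Liver injury is a designated adverse event of special interest in this trial (Sections 5.5.3 and 7.2.4), so the instruction should have only one reading. What is at stake is patient safety and consistent conduct. The efficacy analysis is not touched.

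**Working it through.** There is no sample size, power or error rate to reproduce, so the check is a comparison of rules followed by a short logical test.

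**1. Restart list against the two stop rows**

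| Finding | Table 7 | Section 5.5.3 restart list |
|---|---|---|
| Combined rise, ALP < 2 × ULN, no clear other cause | Permanent stop | Resume at 150 mg once daily on recovery (a); may re-escalate (d) |
| Grade 4 AST, ALT or bilirubin | Permanent stop | The same |
| Recurrence at 150 mg once daily | Not addressed | Discontinue (c) |

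The restart list contains no condition on peak grade, on bilirubin at the time of the event, or on the Table 7 row that was met. Its only ground for stopping FT-2102 is item c. Both stop-row findings fall within its heading.

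**2. Overlap inside Table 7**

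Inputs, all in multiples of ULN: baseline AST/ALT *a0* and bilirubin *t0*; on-treatment values *a* and *t*. Inclusion criterion 7 (Section 4.4.1) admits AST/ALT up to 3.

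- Hold row: *a* > min(max(2·*a0*, 3), 8) and *t* > max(2·*t0*, 2).
- Combined-rise stop row, laboratory part: *a* > 3, *t* > 2, ALP < 2.

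The Hold cut-off for AST/ALT is never below 3, whatever the baseline, and the cut-off for bilirubin is never below 2. Meeting the Hold row therefore always meets the AST/ALT and bilirubin parts of the stop row. At the highest eligible baseline the AST/ALT cut-off is min(max(2 × 3, 3), 8) = 6, so the 8 × ULN alternative does not remove the overlap. Only two things then separate the rows: ALP < 2 × ULN, and the absence of a clear other cause.

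Example: baseline ALT 1.5 and bilirubin 1.0; on treatment ALT 4, bilirubin 2.5, ALP 1.2, no other cause found.

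- Hold row: the ALT cut-off is min(max(2 × 1.5, 3), 8) = 3, and 4 > 3. The bilirubin cut-off is max(2 × 1.0, 2) = 2, and 2.5 > 2. Met.
- Stop row: 4 > 3, 2.5 > 2, 1.2 < 2, no other cause. Met.

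This patient is given both Hold and Permanently discontinue. Neither Table 7 nor the text of Section 6.8.1 says which row governs.

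**The case against.** The best reply is that the texts can be read in harmony. Restarting presupposes an interruption meant to end, and a permanent stop is not one. Section 5.5.3 does not itself order FT-2102 to be held; the hold comes from Table 7, so the restart list most naturally follows the Hold rows. Within Table 7, the stop row adds two conditions and its action is stricter. The Section 5.5.3 work-up is also what shows whether another cause exists, so hold, work up, then stop follows from the row's own terms. This is the sensible reading, and it makes the overlap mild. But it is not written, and the restart heading covers suspected liver injury generally, not held patients.

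Three other texts might seem to settle the matter:

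- **The Grade 4 resume footnote.** Its marker is in Table 6, whose title excludes liver function abnormalities, and no Table 7 cell carries it. It also requires the judgement of Investigator and Sponsor, which the restart list does not.
- **The deviation clause in Section 6.8.1, and the label Recommended on the tables.** These soften the conflict, but a deviation needs a default and none is named.
- **Reporting of hepatic events of special interest to the sponsor within 24 hours.** This may catch a divergence but does not say which instruction applies.

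A reader might go further and infer that the bilirubin condition in the Hold row attaches only to the 8 × ULN alternative, so that the row itself is ambiguous. The text does not support this. The whichever-is-lower wording joins the AST/ALT alternatives into one cut-off, to which bilirubin is then added. At eligible baselines (AST/ALT up to 3 × ULN), a value above 8 × ULN always exceeds twice baseline and 3 × ULN, so that reading would leave the bilirubin condition with no effect.

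**Conclusion.** The point stands, at minor to moderate size. The main defect is that the restart list, as written, covers patients whom Table 7 stops permanently, and nothing in the protocol reconciles the two. The unranked overlap inside Table 7 is secondary.

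The conclusion rests on taking the restart heading at its literal scope. The overlap finding rests on reading the Hold row as one AST/ALT cut-off combined with bilirubin.

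The number of patients who would meet the conflict is unknown. A reader might use the hepatic event rate of about 20% in Section 5.5.3 as its size, but that rate counts any event potentially associated with hepatic dysfunction, not events meeting a stop row. Nor do the documents show that any patient was rechallenged against Table 7. No error rate, estimand or sample size is affected.

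**What to change.** - **Section 5.5.3:** state that the restart steps apply only to events in the Table 7 Hold rows.
- **Table 7:** add that FT-2102 is held during the Section 5.5.3 work-up and permanently stopped if the combined-rise row is met and no other cause is found; that Grade 4 AST, ALT or bilirubin remains a permanent stop; and that the stricter row governs when two apply.

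The cost is a few sentences at the next amendment and a memo to sites, with no new procedures or patients. The downside is that some patients lose the option of rechallenge that a literal reading of Section 5.5.3 now gives them.

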6.8.2 FT-2102 Recommended Dose Reductions

A dose may be withheld up to 28 days (up to 14 days for Cycle 1 only) for toxicity. Doses withheld for > 28 days (> 14 days for Cycle 1 only) may result in discontinuation from the study, unless approved by the medical monitor.

In the Phase 1 dose escalation part of the study: Dose reductions in Cycle 1 are allowed only after a DLT and not below the 150 mg QD.

Recommended dose reductions for all AEs including those associated with LFT abnormalities are outlined in Table 8.

Table 8 Recommended FT-2102 Dose Reduction Levels

Starting Dose	Reduction Level -1
150 mg BID ^a	150 mg QD

a. Patients currently treated with 100 mg BID can further reduce to 150 mg QD if clinically indicated.

Patients who have a dose reduction due to toxicity may be eligible for a dose increase back to the initial dose if the following criteria are met:

- 1. Patient has recovered to baseline levels from the toxicity which caused the dose reduction
- 2. Patient has tolerated the lower treatment dose for > 1 week (or at least 28 days for liver function test abnormality AEs)

Any patient who requires a dose reduction > 1 level below starting dose will be discontinued from the study. Patients who discontinue treatment must be monitored per study procedure and assessment schedule, unless they withdraw consent.

6.8.3 Azacitidine Dose Modifications

Patients enrolled in the combination arm of azacitidine + FT-2102 will be treated at a stable azacitidine dose of 75 mg/m²/day for 7 days consecutively (via subcutaneous injection or intravenous infusion), but a 48-hour dose interruption for weekends or holidays is allowed. Azacitidine is to be administered beginning on Cycle 1 Day 1 and then Day 1 of each subsequent 28-day treatment cycle. Alternate schedules for the start of azacitidine administration (e.g., beginning on Day 8 of each treatment cycle) is accepted when clinically indicated at the investigator's discretion.

Patients who are unable or unwilling to continue treatment with azacitidine after the first treatment cycle may continue participation in the study taking FT-2102 alone, at the discretion of the investigator. During Cycle 1, in dose escalation cohorts only, patients who do not receive at least 75% of their scheduled dose due to drug toxicity (dose hold) will have that counted towards the criteria for a DLT.

Azacitidine dose adjustment may be more or less conservative per investigator's discretion according to the local institutional guidelines.

6.8.3.1 Azacitidine Dose Adjustment Based on Hematology Laboratory Values

Azacitidine dose modifications based on hematology laboratory values are presented in Table 9.

For patients with baseline (start of treatment) WBC \geq 3.0 x 10⁹/L, ANC \geq 1.5 x 10⁹/L, and platelets \geq 75.0 x 10⁹/L, adjust the dose as shown in Table 9A, based on nadir counts for any given cycle. For patients whose baseline counts are WBC < 3.0 × 10⁹/L, ANC < 1.5 × 10⁹/L, or platelets < 75.0 × 10⁹/L, dose adjustments should be based on nadir counts and bone marrow cellularity at the time of the nadir as shown in Table 9B, unless there is clear improvement in differentiation (percentage of mature granulocytes is higher and ANC is higher than at onset of that course) at the time of the next cycle, in which case the dose of the current treatment should be continued.

Table 9 Azacitidine Dose Modifications: Hematology Laboratory Values

A – Baseline WBC \geq 3.0 x 10 9 /L, ANC \geq 1.5 x 10 9 /L, and platelets \geq 75.0 x 10 9 /L										
Nadi	ir Counts	0/	Daniel de Nant Carre							
ANC (x10 ⁹ /L)	Platelets (x10 ⁹ /L)	9/0	% Dose in the Next Course							
< 0.5	< 25.0		50%							
0.5 – 1.5	25.0 - 50.0		67%							
> 1.5	> 50.0	100%								
B – Baseline WBC	$C < 3.0 \times 10^9/L$, ANC < 1.6	5 × 10 ⁹ /L, or platelets <	< 75.0 × 10 ⁹ /L							
WBC or Platelet N		Bone Marrow Cellularity at time of nadir (%)								
Percent decrease i	n counts from Baseline	30 – 60	15 – 30	< 15						
		Percent dose in the next course								
5	0 - 75	100	50	33						
	> 75	75	50	33						

ANC = absolute neutrophil count; WBC = white blood cell (count).

If a nadir as defined in the table above has occurred, the next course of treatment should be given 28 days after the start of the preceding course, provided that both the WBC and the platelet counts are > 25% above the nadir and rising. If a > 25% increase above the nadir is not seen by Day 28, counts should be reassessed every seven days. If a 25% increase is not seen by Day 42, then the patient should be treated with 50% of the scheduled dose.

In patients achieving CRi, if the incomplete hematological recovery is considered to be related to azacitidine, dose reduction and treatment interruptions may be considered at the investigator's discretion.

6.8.3.2 Dose Adjustment of Azacitidine Based on Serum Electrolytes and Renal Toxicity

If unexplained reductions in serum bicarbonate levels to < 20 mEq/L occur, the dosage should be reduced by 50% on the next course. Similarly, if unexplained elevations of BUN or serum creatinine occur, the next cycle should be delayed until values return to normal or baseline and the dose should be reduced by 50% on the next treatment course. In addition, the laboratory parameters that resulted in the dose delay or reduction should be rechecked twice weekly until they return to baseline or grade 1 level, whichever is worse.

6.8.4 Cytarabine

Patients enrolled in the Phase 1 combination cohort of cytarabine + FT-2102 will be treated at a flat dose of 20 mg BID of cytarabine given subcutaneously (SC) for 10 days every 28-day cycle.

Cytarabine dosing delays and interruptions for adverse events are allowed at the Investigator's discretion.

Patients who are unable or unwilling to continue treatment with LDAC after the first treatment cycle may continue participation in the study taking FT-2102 alone, at the discretion of the investigator. During Cycle 1, patients who do not receive their scheduled dose due to drug toxicity (resulting in dose hold) will have that counted towards the criteria for a DLT.

7 PROCEDURES FOR REPORTING ADVERSE EVENTS

7.1 Adverse Events Definitions

The Investigator will monitor the occurrence of AEs during the course of the study and for 28 days after the administration of the last dose of study drug.

The following definitions of terms are guided by the International Council on Harmonisation and the United States Code of Federal Regulations and are included here verbatim.

Adverse event is any untoward medical occurrence in a patient or clinical investigation patient administered a pharmaceutical product that does not necessarily have a causal relationship with this treatment.

Serious Adverse Event is any adverse event that results in any of the following outcomes: Death, a life-threatening event, inpatient hospitalization or prolongation of existing hospitalization, a persistent or significant disability/incapacity, or a congenital anomaly/birth defect.

Important medical events that may not result in death, be life-threatening, or require hospitalization may be considered a serious adverse event when, based upon appropriate medical judgment, they may jeopardize the patient or subject and may require medical or surgical intervention to prevent one of the outcomes listed in this definition.

Life-threatening refers to any adverse event that places the patient or subject, in the view of the Investigator, at immediate risk of death from the reaction as it occurred (i.e., it does not include a reaction that, had it occurred in a more severe form, might have caused death).

Associated with the use of the drug means that there is a reasonable possibility that the experience (event) may have been caused by the drug.

Unexpected adverse event means any adverse event, the specificity or severity of which is not consistent with those listed in the current Investigator's Brochure (IB).

7.2 Reporting of Adverse Events

7.2.1 Adverse Events

Refer to Section 6.2.1 for a summary of ongoing safety review during the study, including review of any new Suspected Unexpected Serious Adverse Reactions (SUSARs).

Serious AEs (SAEs) will be collected from the time the patient signs the informed consent form until 28 days after the last dose of study drug, or until the initiation of an investigational agent or cytotoxic chemotherapy, whichever comes first, and as per Section 7.2.3. Serious AEs will be collected on the Adverse Event eCRF from the time of first dose of study drug until 28 days after the last dose of study drug, or until the initiation of an investigational agent or cytotoxic chemotherapy, whichever comes first.

Adverse Events of Special Interest (AESI), as defined in Section 7.2.4, should be collected on the AESI Form from the time of first dose of study drug until 28 days after the last dose of study drug and reported to Forma Therapeutics Pharmacovigilance within 24 hours of knowledge of event.

Non-serious adverse events will be collected and reported on the Adverse Event eCRF from the time of the first dose of study drug until 28 days after the last dose of study drug, or until the initiation of an investigational agent or cytotoxic chemotherapy, whichever comes first.

Patients withdrawn from the study because of AEs will be followed by the Investigator until the outcome is determined. When appropriate, additional written reports and documentation will be provided.

All AEs beginning after the last exposure of study drug must be reported to the Sponsor or its designee if the onset of the AE was within 28 days of the last exposure to study drug. All AEs, whether serious or nonserious, that are judged by the Investigator to be at least possibly related to study drug administration must be reported to the Sponsor or its designee regardless of how much time has elapsed since the last exposure to study drug (i.e., beyond 28 days of the last exposure to study drug).

